4.2.1 Primary Effectiveness Endpoint

The primary effectiveness endpoint is the change from baseline to the 4-weeks follow up exam in Tear Break-Up Time (TBUT). TBUT must be assessed by a masked rater. The changes from baseline will be evaluated.

4.2.2 Secondary Effectiveness Endpoints

- Change from baseline in patient symptoms using the Ocular Surface Disease Index (OSDI) at the 4-weeks and 12 weeks follow-up exam. OSDI is a scoring that evaluates patient symptoms based on a validated questionnaire [4].
- Changes from baseline to 4-weeks and the 12-weeks follow-up exam in Meibomian Gland Score (MGS). MGS must be assessed by a masked rater.

The MGS is determined for the lower eyelids using a device that applies a standardized pressure to an area including 5 glands (Meibomian Gland Evaluator, Johnson & Johnson Vision) while viewing the eyelid margin using a slit lamp microscope to determine the presence and quality of the gland secretions. A total of 15 glands in three lower eyelid zones (nasal, medial, temporal) will be evaluated. Each gland is graded from 0 to 3 (0 = no secretion, 1 = inspissated, 2 = cloudy, 3 = clear liquid). The maximum MGS score is 45 in each eye. The clinician performing the MGS must not be involved in the study procedure and must be blinded to which arm of the study the patient is randomized.

• Change from baseline to the 12-weeks follow-up exam in Tear Break Up Times (TBUT), as assessed by a masked rater.

4.2.3 Primary Safety Endpoint

The primary safety endpoint will be a comparison of the incidence of device-related adverse events (e.g., increase in the lid margin such as development of floppy eyelids, entropion or ectropion; and lash integrity) for the two-treatment arms.

4.2.4 Secondary Safety Endpoints

Secondary safety endpoints will be the following assessments:

- The evaluation of discomfort and pain during treatment
- Changes from baseline following treatment for the test and control devices for the following assessments:
 - o Ocular Surface Staining
 - o Intraocular Pressure
 - o Cornea OCT evaluation to detect changes (cornea thickness, cornea deamination) following treatment- will be performed on a subset of 10 patients, who first enrolled, only in the Tixel arm (since LP has a protective cup on the cornea).

5 PATIENT POPULATION

The study will include adult patients with symptoms of MGD/evaporative dry eye.

5.1 Inclusion Criteria

- 1. Age 18 years and older of any gender or race.
- 2. Provision of written informed consent prior to study participation.
- 3. Willingness and ability to return for all study visits.
- A positive history of self-reported dry eye symptoms for three months prior to the study using the Ocular Surface Disease Index (OSDI) questionnaire, and a score of ≥ 23 at the baseline visit.
- Evidence of meibomian gland (MG) obstruction, based on a total Meibomian Gland Score (MGS) of ≤12 in the lower eyelids for each eye. The rater of MGS must not be involved in the study procedure.
- 6. Non-invasive tear break-up time (TBUT) <10 seconds in both eyes. The rater of TBUT must not be involved in the study procedure.
- 7. Agreement/ability to abstain from dry eye/MGD medications for the time between the treatment visit and the final study visit. Ocular lubricants are allowed if no changes are made during the study.
- 8. Fitzpatrick skin type I-VI.

5.2 Exclusion Criteria

- 1. History of ocular surgery including intraocular, oculo-plastic, corneal or refractive surgery within 1 year.
- 2. Patient with giant papillary conjunctivitis.
- 3. Patient with punctal plugs or who have had punctal cautery.
- 4. Ocular injury or trauma, chemical burns, or limbal stem cell deficiency within 3 months of the baseline examination.
- 5. Active ocular herpes zoster or simplex of eye or eyelid or a history of these within the last 3 months.
- 6. Patient who are aphakic.
- 7. Cicatricial lid margin disease identified via slit lamp examination, including pemphigoid, symblepharon, etc.
- 8. Active ocular infection (e.g., viral, bacterial, mycobacterial, protozoan, or fungal infection of the cornea, conjunctiva, lacrimal gland, lacrimal sac, or eyelids including a hordeolum or stye).

- 9. Active ocular inflammation or history of chronic, recurrent ocular inflammation within prior 3 months (e.g. retinitis, macular inflammation, choroiditis, uveitis, iritis, scleritis, episcleritis, keratitis).
- 10. Ocular surface abnormality that may compromise corneal integrity (e.g., prior chemical burn, recurrent corneal erosion, corneal epithelial defect, Grade 3 corneal fluorescein staining, or map dot fingerprint dystrophy).
- 11. Lid surface abnormalities (e.g., entropion, ectropion, tumor, edema, blepharospasm, lagophthalmos, severe trichiasis, severe ptosis) that affect lid function in either eye.
- 12. Anterior blepharitis (staphylococcal, demodex or seborrheic grade 3 or 4).
- 13. Systemic disease conditions that cause dry eye (e.g., Stevens- Johnson syndrome, vitamin A deficiency, rheumatoid arthritis, Wegener's granulomatosis, sarcoidosis, leukemia, Riley-Day syndrome, systemic lupus erythematosus, Sjogren's syndrome).
- 14. Unwillingness to abstain from systemic medications known to cause dryness for the study duration.
- 15. Women in child baring age who are pregnant, nursing, or not utilizing adequate birth control measures.
- 16. Individuals who have either changed the dosing of systemic or non-dry eye/MGD ophthalmic medication within the past 30 days prior to screening.
- 17. Individuals who are unable or unwilling to remain on a stable dosing regimen for the duration of the study.
- 18. Individuals using isotretinoin (Accutane) within 1 year, cyclosporine-A (Restasis) or lifitegrast ophthalmic solution (Xiidra) within 3 months, or any other dry eye or MGD medications (antibiotics, non-steroidal anti-inflammatory drugs, corticosteroids) for at least 2 weeks and to maintain abstinence throughout the duration of the study (ocular lubricants are allowed if no changes are made during the study).
- 19. Individuals wearing contact lenses at any time during the prior three months and at any point during the study.
- 20. Current skin cancer, malignant sites and/or advanced premalignant lesions or moles in the treatment area.
- 21. An impaired immune system condition or use of immunosuppressive medication.
- 22. Collagen disorders, keloid formation and/or abnormal wound healing.
- 23. Previous invasive/ablative procedures in the areas to be treated within 3 months prior to initial treatment or plans for such treatment during the course treatment, or before complete healing of such treatments has occurred.

- 24. Any patient who takes or has taken any oral or topical medications, herbal treatments, food supplements, or vitamins which may cause fragile skin or impaired skin healing during the last 3 months.
- 25. Any patient who has a history of bleeding coagulopathies.
- 26. Any patient who has tattoos or permanent makeup in the treated area.
- 27. Any patient who has burned, blistered, irritated, or sensitive skin in any of the areas to be treated.
- 28. Individuals using another ophthalmic investigational device or agent within 30 days of study participation.
- 29. Individuals that were treated with LipiFlow in the last 24 months, or Tixel at any point in the past.
- 30. Treatment in either eye with IPL in the last year.
- 31. Expression of the meibomian glands within 6 months prior to screening.
- 32. Use of at home warm compresses or lid hygiene products while participating in study.

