1 INTRODUCTION

1.1 Background

Dry Eye Disease (DED) is often caused by a chronic lack of sufficient lubrication and moisture on the surface of the eye. Consequences of dry eyes range from subtle to constant eye irritation, significant inflammation and even scarring of the front surface of the eye.

Meibomian glands are located in the tarsal plate of the upper and lower eyelids, where they terminate along the interior rim (or margin) of the eyelids. These glands secrete meibum, which is a lipid-rich essential component of a healthy tear film. When sufficient meibum is not present in the tear film, the aqueous layer of the tear film is disrupted and readily evaporates causing irritation, redness, and inflammation of the lid margin and surrounding tissues. Meibomian Gland Dysfunction (MGD) is associated with a failure of these glands to produce adequate quantities of meibum due to atrophy, inflammation, or obstruction and is thought to be the most common cause of evaporative Dry Eye Disease [1; Schaumberg DK 2011].

Initial treatments for the signs and symptoms related to MGD and DED are the use of oil-based artificial tears to supplement the lack of lipid in the tear layer and oral Omega and antiinflammatory prescriptions to decrease inflammation in the soft tissue in the eyelids. Another common treatment is the use of warm compresses applied over the eyelid for extended periods of time, followed by digital massage of the glands by the patient to try and express oil from the meibomian glands. The results of these treatments are often limited and temporary if not continued on a regular basis.

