8.1.3 General Examination

A general clinical examination is required to assess eligibility. This examination will include demographics information, past medical and ocular history, known allergies, use of Concomitant Systemic and Ophthalmic Medications and patient's report of the daily usage (frequency and dose) of eye lubricants.

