6.5 Treatments

The study procedure in both study arms shall be performed on both eyes on the same day.

Testing must be done in the following order:

- Concomitant systemic and ophthalmic medications (before treatment 1, only if not done during screening).
- Patient's report of the daily usage (frequency and dose) of eye lubricants. Before treatment 1, only if not done during screening. If data was collected at screening, only changes will be collected.

Before treatments 2 and 3 in the Tixel arm- patient's report will be collected since the last treatment done.

Before treatment 1, only for 10 patients randomized to a sub-set of the Tixel arm: Cornea
OCT and coded images upload to EDC and/or SharePoint. OCT assessment should be
performed before any corneal testing.

The following tests may be done again before treatment #1, only if treatment is being done on a different day than baseline exam, at the discretion of the investigator (these tests will be done prior to treatments 2 and 3 for the Tixel arm):

- Slit Lamp for Anterior Segment
- Lid Margin Abnormalities
- Eyelid Margin Assessment
- 1. Eye makeup shall be removed.
- The device shall be prepared for use in accordance with the Instructions for Use (IFU)/User Manual for the device to which the patient is randomized. An IFU/User Manual is packaged with each device that will be used in the study.
- For the LipiFlow treatment- Anesthetic eye drops shall be applied as per the Testing Methodologies for CLN 0798 study (CLN_0802).
- 4. For the Tixel treatment-Anesthetic cream/gel may be applied only on the eyelids according to the investigator discretion.
- Therapy shall be delivered in accordance with the IFU/User Manual for the device to which the patient is randomized. Refer to the Testing Methodologies for CLN 0798 study (CLN_0802) for more information.
- 6. For Tixel device treatment, the following zones will be treated at the following Parameters: Small tip, 6 milliseconds pulse duration, 400μm protrusion, single pulse in the following order:
 - 5 shots nasal, medial, temporal region directly below/above lid margin next to each other (Figure 4)
 - 5 shots a little lower/higher (Figure 4)

Figure 4-Treatment Zones With Tixel

7. Representatives from the Sponsor may be present during the study visits when required.

- 8. Throughout the treatment visit, patients will be assessed for any adverse events, including for development of entropion or ectropion, floppy eyelids, and lash integrity assessment.

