7 STATISTICAL CONSIDERATIONS

7.1 General Considerations

Descriptive statistics will be used to summarize continuous variables (number of eyes/patients [N], mean, standard deviation (SD) or standard error of the mean, median, maximum, and minimum) and categorical variables (frequency and percentage) at each assessment timepoint. Statistical comparisons within each group will be performed using appropriate statistical methods or models, and the results such as 95% confidence intervals and p values will be reported. All summary tables will be supported with individual patient and eye data listings. Baseline is defined as the last non-missing observation prior to initiation of study intervention. Analyses will be carried out using SAS software or equivalent statistical software.

Further details will be described in the statistical analysis plan, which will be finalized prior to the study database lock.

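### The 30-day stable-dose rule before screening does not reach ocular lubricants, so a recent lubricant change can carry over into the within-arm primary result

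*Combined protocol and SAP*

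**What the plan says.** Four eligibility rules bear on this.

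- Section 5.2, exclusion 16, looks back from screening. It excludes "Individuals who have either changed the dosing of systemic or non-dry eye/MGD ophthalmic medication within the past 30 days prior to screening".
- Section 5.1, inclusion 7, looks forward: "Ocular lubricants are allowed if no changes are made during the study".
- Section 5.2, exclusion 18, sets washouts for other dry-eye drugs and repeats the exception: "ocular lubricants are allowed if no changes are made during the study".
- Section 5.2, exclusion 17, also looks forward: "Individuals who are unable or unwilling to remain on a stable dosing regimen for the duration of the study".

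The background (section 1.1) treats artificial tears as therapy for this disease: "Initial treatments for the signs and symptoms related to MGD and DED are the use of oil-based artificial tears".

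On data, section 8.1.3 takes the "patient's report of the daily usage (frequency and dose) of eye lubricants" at screening. Section 6.5 adds, for the first treatment visit, "If data was collected at screening, only changes will be collected". Lubricant use is reported again at both follow-up visits (sections 6.6 and 6.7).

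On analysis, section 7.1 states "Baseline is defined as the last non-missing observation prior to initiation of study intervention". Section 7.4 tests the change in TBUT at 4 weeks inside each arm, by paired t-test or signed rank test. It describes no lubricant covariate and no sensitivity analysis on lubricant use.

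**The concern.** The plan asks for 30 days of unchanged dosing for eye drugs that have nothing to do with dry eye, but sets no such period for the dry-eye product that patients may keep using. The gap is there on either reading of the wording. If lubricants are dry-eye products, as section 1.1 implies, the phrase in exclusion 16 leaves them out. If a site regards them as not being medication, exclusion 16 does not reach them at all.

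The design is exposed to this because the primary test is a within-arm change and neither arm is untreated or sham-treated. If a patient's response to a new lubricant regimen is incomplete at baseline and continues afterwards, the remainder enters the change score and nothing in the primary analysis separates it from the device. Keeping lubricant use unchanged during the study does not help, since the change came before it.

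**Working it through.** **Inputs from the documents.** 15 patients per arm; expected change 1.5 s; SD of the change 1.9 s; paired t-test, two-sided 0.05 (all section 7.7).

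**Inputs that are assumptions.** k, the number of patients in an arm with a recent lubricant change, and g, the further TBUT gain per such patient after baseline. The documents give neither.

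**Step 1: reproduce the plan's figure.** Standard error = 1.9/√15 = 0.491 s. Noncentrality = 1.5/0.491 = 3.06 on 14 degrees of freedom. The exact noncentral-t power is 0.811 (0.802 with the rounded effect size of 0.78), and 15 is the smallest sample that reaches 80%. Section 7.7 is therefore consistent with a test against zero change.

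**Step 2: effect of a residual lubricant gain when the device does nothing.** Mean shift = (k/15) × g, and noncentrality = shift/0.491. The two-sided rejection rate against zero is:

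| k of 15 | g (s) | Shift (s) | Noncentrality | False-positive rate |
|---|---|---|---|---|
| 0 | – | 0 | 0 | 5.0% |
| 3 | 0.5 | 0.10 | 0.20 | 5.4% |
| 5 | 0.5 | 0.17 | 0.34 | 6.2% |
| 3 | 1.0 | 0.20 | 0.41 | 6.7% |
| 5 | 1.0 | 0.33 | 0.68 | 9.7% |
| 7 | 1.0 | 0.47 | 0.95 | 14.4% |

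These rates apply the mean shift to everyone. If only the k patients gain, the spread also rises and the rates fall a little: simulation gives about 8.6% instead of 9.7% for 5 of 15 gaining 1.0 s.

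**Step 3: scale.** A 0.10 s shift is 0.10/1.5 = 7% of the planned change; 0.33 s is 22%. If the lubricant is already having its full effect at baseline, g = 0 and there is no bias. If g is negative, the same shift acts against the device.

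**Step 4: the other null.** Section 7.4 prints a primary null of less than 1.5 s. Under that null, with no device effect and a 0.33 s shift, the noncentrality is (0.33 − 1.5)/0.491 = −2.38, and the chance of a false success is below 0.01%.

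**Step 5: can the current data show who is affected?** Section 8.1.3 records current frequency and dose, and section 6.5 records changes from screening onwards. Neither asks when use started or last changed, so stability before screening cannot be confirmed from them.

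**The case against.** A reader might infer that the plan itself makes a late switch likely, because exclusion 18 takes patients off other dry-eye drugs and they may turn to drops instead. The text does not support that. The washouts are at least 2 weeks for other dry-eye or MGD drugs, 3 months for cyclosporine or lifitegrast, and 1 year for isotretinoin. A patient who substitutes drops would most naturally do so on stopping the drug, which leaves weeks or months for the drops to settle. A patient only 2 weeks off a drug might also still be losing its benefit, which would pull the change downward. Neither frequency nor direction is settled.

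The larger illustrations are also generous. A further 1.0 s from lubricant alone exceeds the only change without active device treatment that the protocol quotes, 0.75 s for sham plus gland expression (section 1.3). Section 1.1 describes the results of initial treatments as often limited. Nothing says that lubricants act slowly enough to leave a gain after baseline.

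It is fair to add that lubricant use is tracked during the study, and that randomisation balances recent changers between arms in expectation. That balance helps the secondary Tixel–LipiFlow comparison but not the within-arm primary test. It is incomplete even there: chance imbalance is possible with 15 per arm, and by section 6.4 the 4-week exam falls about 8 weeks after Day 0 for Tixel and about 4 weeks for LipiFlow.

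These arguments limit the likely size and priority. They do not close the gap in the eligibility text.

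**Conclusion.** The gap is real and the point is minor. No provision requires lubricant use to be stable before baseline, and the within-arm primary test cannot remove an effect that is still developing. The possible inflation runs from nothing, through 5.4% (3 of 15 gaining 0.5 s), to 9.7% (5 of 15 gaining 1.0 s). It rests on assumed counts and gains and on a test against zero, which is how section 7.7 sizes the trial. Under the 1.5 s null printed in section 7.4 it is negligible.

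The tempting stronger conclusion is that recent lubricant changes will bias the primary result towards the device. The documents do not support it. They permit the bias but give no evidence of its frequency, size or sign. The sample size and power in section 7.7 are unaffected.

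**What to change.** - In section 5.2, extend the existing 30-day pre-screening stability rule of exclusion 16 to ocular lubricants, naming product, frequency and dose. Thirty days is the plan's own period; if the sponsor wants another length for lubricants, it should state it.
- Align the lubricant wording of inclusion 7 and exclusion 18, so that the no-change condition covers the same period before screening as well as the study itself.
- In section 8.1.3, add the date of the last lubricant change (or start) to the usage report. Without it the rule cannot be checked.

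The cost is a few words in sections 5.1 and 5.2, one extra data item at screening, and a short delay for recent changers until the period is complete. The analysis and sample size need no change.

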6 STUDY PROCEDURES

6.1 Patient Screening and Enrolment

Patients will be screened, assessed, treated and followed according to the schedule of events in Appendix A. Patients must have the study explained to them by the Investigator/Subinvestigator (or other delegated study team if allowed by local regulations), they must be provided sufficient time to consider their participation in the study and provided an opportunity to ask questions of the study team. Patients must sign the most current version of an informed consent form (ICF) approved by an Institutional Review Board (IRB)/Ethics committee. All patients who sign an ICF and meet the entire protocol criteria are considered enrolled patients in the study; if not, they will be considered as screen-failures. Therefore, patients should be pre-screened to the extent possible prior to signing an ICF, but patients should not undergo any study-specific assessments until they have signed the ICF.

6.1.1 Informed Consent

During the informed consent (IC) process with the patient, the study investigator or designee will explain the purpose of the study, the possible risks and benefits, and the schedule of visits required for participation. The study investigator or designee will explain to the patient that,

after signing the IC form, the patient may not be found eligible to participate in the study if he/she doesn't meet all inclusion/exclusion criteria.

The patient may take the IC form and consult with their family, friends or doctor. After reading and understanding the IC, if the patient decides that he/she wishes to participate in the study, he/she should return, with a signed IC form at which time he/she will undergo specific tests as specified in Appendix A. These tests will be done only after the patient signed the ICF, clearly indicating his/her understanding of the requirements and risks involved with study participation and other applicable treatment options.

6.1.2 Patient Identification

At the screening, the patient will receive a unique identifying Patient ID number that will be composed of the site number (2 digits) and a three-digit consecutive patient number. This unique Patient ID will be used throughout the entire study and will be entered in the patient's eCRFs for the screening visit, baseline visit, each treatment visit and the follow-up visits.

8.1.3 General Examination

A general clinical examination is required to assess eligibility. This examination will include demographics information, past medical and ocular history, known allergies, use of Concomitant Systemic and Ophthalmic Medications and patient's report of the daily usage (frequency and dose) of eye lubricants.

8.1.4 Fitzpatrick Skin Type

The Fitzpatrick skin type will be determined according to genetic disposition, reaction to sun exposure and tanning habits. The Fitzpatrick scale classifies 6 skin types, as summarized below. In this study, all Fitzpatrick skin types I-VI are eligible to participate, consistent with the device labelling.

TYPE I: Highly sensitive, always burns, never tans. Example: Red hair with freckles

TYPE II: Very sun sensitive, burns easily, tans minimally. Example: Fair skinned, fair haired Caucasians

TYPE III: Sun sensitive skin, sometimes burns, slowly tans to light brown. Example: Darker Caucasians.

TYPE IV: Minimally sun sensitive, burns minimally, always tans to moderate brown. Example: Mediterranean type Caucasians, some Hispanics.

TYPE V: Sun insensitive skin, rarely burns, tans well. Example: Some Hispanics, some Blacks

TYPE VI: Sun insensitive, never burns, deeply pigmented. Example: Darker Blacks.

6.2 **Pre-Treatment/Baseline Assessments**

The following assessments will be performed at the baseline visit, for both treatment arms, prior to treatment (Note: The OSDI must be administered self-assessed prior to clinical evaluations). The detailed instructions can be found in the Testing Methodologies for CLN 0798 study (CLN_0802).

Assessment	Description
OSDI	Scoring that evaluates patient symptoms based on a validated
	questionnaire [2 Schiffman RM, 2000]. (OSDI Questionnaire
	provided in Appendix B). OSDI questionnaires include 12
	questions in 3 categories. The questionnaire is self- assessed
	where patients are asked to circle a number next to a
	description that best represents their answer on a paper form.
	The numbers for each category are totalled and the total OSDI
	score is calculated by the formula: sum of scores x $25/\#$ of
	questions answered. Dry eye severity is then assessed using
	the chart on the 2nd page of the questionnaire.
Uncorrected Distance	Patient will be seated with no glasses in front of a Snellen
Visual Acuity	vision chart that is calibrated to measure at 6 meters.
Corrected Distance Visual	If patient does not regularly wear glasses for distance this test
Acuity	will not be done.
	The patient will be seated with glasses (if worn) in front of a
	Snellen vision chart that is calibrated to measure at 6 meters.
Keratometry	Test of corneal curvature conducted using a manual
	keratometer or simulated keratometry from corneal
	topography.
Slit Lamp for Anterior	Using biomicroscopy to examine anterior segment including
Segment Health	lids, adnexa, conjunctiva, sclera, corneal clarity, and surface
	integrity, anterior chamber, and iris. Grading system:

Table 1-Patient Assessments

	• 0=No clinical findings
	• 1=Non-clinically significant positive findings (including
	pterygium, pinguecula, corneal scar, conjunctival pigment,
	corneal arcus, verucca, non-visual significant lens changes)
	• 2=Abnormal findings
Lid Margin Abnormalities	Scored 0-4 based on the number of the following present in
	each eye:
	• irregular lid margin
	• vascular engorgement
	plugged meibomian gland orifices
	• anterior or posterior replacement of the mucocutaneous
	junction
Eyelid Margin Assessment	Development of any of the following: • entropion or ectropion
	• floppy eyelids • loss of lash integrity
Tear Break-Up Time	Note: TBUT Assessments must be made by a rater not
(TBUT)	involved in the study procedure and blinded to the arm to
	which the patient is randomized
	• Use one Fluorescein strip per eye
	• Apply one or two drops of non-preserved saline to
	the impregnated paper tip. Excess fluid will
	automatically fall off. Shaking is neither required nor desirable
	 Ask the patient to look down and in
	• Gently touch the strip to the superior temporal bulbar
	conjunctiva for one or two seconds
	Ask the patient to blink three times and open eyes neturally
	naturallyImmediately measure the time between the last blink
	and the first appearance of a dark spot on the cornea
	(formation of dry area)
	• Time shall be recorded in seconds and shall be the
	average of three consecutive measurements Period average of three consecutive measurements
	• Repeat with a new strip for the second eye

Corneal Fluorescein Staining Slit Lamp Evaluation	 Use one Fluorescein strip per eye. Apply 1-2 drops of non-preserved saline to the impregnated paper tip. Excess fluid will automatically fall off. Shaking is neither required nor Desirable. Ask the patient to look down and in. Gently touch the strip to the superior temporal bulbar conjunctiva for one or two seconds. Start with low illumination and gradually increase until staining is visible. Grade each region according to the National Eye Institute corneal grading below and record the Total Score for each eye. Score will range from 0 to 15. National Eye Institute (NEI) corneal grading scale evaluating five corneal regions: superior inferior central temporal nasal Each graded on a 0-3 scale (0=normal-no staining; 1=mild-superficial stippling micropunctate staining; 2=moderate-macropunctate staining with some coalescent areas; 3=severe-numerous coalescent macropunctate areas and/or patches) [3
Conjunctival staining Lissamine green	 Use one Lissamine green strip per eye. Apply 1-2 drops of non-preserved saline to the impregnated paper tip. Excess fluid will automatically fall off. Shaking is neither required nor desirable. Ask the patient to look down and in. Gently touch the strip to the superior temporal bulbar conjunctiva for one or two seconds. Wait at least 1 minute before grading the conjunctival staining. Perform grading within 4 minutes of instilling the dye. Start with low illumination and gradually increase

	 until staining is visible. Record the grade (0-3) of each of the regions (nasal, superior nasal, inferior nasal, temporal, superior temporal, inferior temporal) and record the Total Score for each eye. Score will range from 0 to 18. (0=normal-no staining; 1=mild-superficial stippling micropunctate staining; 2=moderate-macropunctate
	 staining with some coalescent areas; 3=severe- numerous coalescent macropunctate areas and/or patches). Make sure to identify pooling or a stained mucus strand. Ask patients to blink a couple of times when in doubt.
Meibomian Gland	Note : Meibomian Gland Assessments must be made by a rater
Assessment and Scoring	not involved in the study procedure and blinded to the arm to which the patient is randomized.
	• Assess lower eyelids using Meibomian Gland Evaluator
	while viewing the eyelid margin using slit lamp microscope
	• Evaluate 15 glands in 3 zones (nasal, medial, temporal)
	• Each gland graded from 0 to 3
	• Maximum MGS score=45 in each eye
	[4 Lane SS. 2012, 5 Blackie CA. 2015]
Intraocular Pressure	Measured by a Goldmann tonometer and recorded in mmHg
Optical Coherence	OCT assessment should be performed before any corneal
Tomography (OCT)	testing. Cornea OCT evaluation will be done to detect
(Will be done only after	changes (cornea thickness, cornea deamination) between
randomization)	baseline and following treatments- will be performed after
, 	randomization, on a subset of 10 patients (the first 10
	enrolled patients), only in the Tixel arm. Images will be
	coded with site number, patient screening number, visit
	number and left/right eye and will be uploaded to EDC
	and/or SharePoint.

